4.1 Subject Inclusion Criteria

Subjects will be included in this study if they meet the following requirements:

- 1. Male or female at least 18 years of age and of any race
- 2. In good general health
- Read, understand and sign the ICF
- 4. If female of child-bearing potential, are willing to use an acceptable method of contraception to prevent pregnancy (i.e. oral contraceptive, intra-uterine device, diaphragm, condom, abstinence, bilateral tubal ligation, or are in a monogamous relationship with a partner who has had a vasectomy)
- 5. Female subjects of child-bearing potential, must have a negative Urine Pregnancy Test (UPT) on Treatment Day prior to any applications of the study products

4.2 Subject Exclusion Criteria

Potential subjects will be excluded from participation if any one of the following criteria apply to them.

- 1. Exposure of test sites to antimicrobial agents, medicated soaps, medicated shampoos, or medicated lotions, use of biocide-treated pools or hot tubs, use of tanning beds, or sunbathing during the 14-day washout conditioning period and during the test period
- 2. Exposure of the test sites to strong detergents, solvents, or other irritants during the 14-day washout conditioning period and during the test period
- 3. Wear fabric softener, bug repellent or UV-treated clothing during the 14-day washout conditioning period and during the test period
- 4. Receive an irritation score of 1 (any redness, swelling, rash, or dryness present at any treatment area) for any individual skin condition prior to the Treatment Day baseline sample collection
- 5. Use of systemic or topical antibiotic medications, steroid medications (other than for hormonal contraception or post-menopausal reasons), or any other product known to affect the normal microbial flora of the skin during the 14-day washout conditioning period and during the test period
- 6. Known allergies or sensitivities to vinyl, latex (rubber), alcohols, metals, inks, or tape adhesives, or to common antibacterial agents found in soaps, lotions, or ointments, particularly isopropyl alcohol or chlorhexidine gluconate
- 7. A medical diagnosis of a physical condition, such as a current or recent severe illness, asthma, diabetes, hepatitis, an organ transplant, mitral valve prolapses, congenital heart disease, internal prostheses, or any immunocompromised conditions such as AIDS (or HIV positive)
- 8. Pregnancy, plans to become pregnant within the washout and test periods of the study, or nursing a child
- 9. Any tattoos or scars within 2" (5.08 cm) of the test sites
- 10. Dermatoses, cuts, lesions, active skin rashes, or breaks or other skin disorders within 6" on or around the test sites
- 11. A currently active skin disease or inflammatory skin condition (for example, contact dermatitis) anywhere on the body that, in the opinion of the Consulting Physician or PI, would compromise subject safety or study integrity
- 12. Showering, bathing, or swimming within the 72-hour period prior to sampling for Treatment Day, and throughout the test period
- 13. Participation in another clinical study in the past 30 days or current participation in another clinical study at time of signing informed consent
- 14. Any medical condition or use of any medications that, in the opinion of the PI, should preclude participation
- 15. Unwillingness to fulfill the performance requirements of the study.

4.3 Subject Consent

The PI or designated sub-investigator trained by the PI must ensure that written informed consent to participate in the investigation is obtained before including any individual as a subject in the investigation. The PI or designated sub-investigator trained by the PI must provide the prospective subject sufficient opportunity to consider whether or not to participate and minimize the possibility of coercion or undue influence.

The process is designed to:

- 1) give the subject all the information needed,
- 2) ensure that the subject understands the information,
- 3) give the subject a chance to consider study participation.

The process should permit the subject to ask questions and exchange information freely.

Specifically, the PI or designated sub-investigator trained by the PI is to explain to each subject all elements of ICF as specified in 21 CFR 50.25. After the explanation, subjects will voluntarily sign and

date the ICF if they wish to participate in the study. A copy of the ICF must be provided to the subject. A signed and dated ICF must be maintained in the PI study documentation file at all times.

5 Study Treatment

These study procedures are based on the American Society for Testing and Materials (ASTM) "Standard Test Method for Evaluation of Preoperative, Precatheterization, or Preinjection Skin Preparations" (E1173-15).

5.1 Study Procedures

5.1.1 Washout Period

The Inclusion/Exclusion Criteria will be reviewed with each subject to ensure eligibility for the study after subjects has signed the ICF.

A skin irritation assessment using the scale from Appendix 17.6 will be performed by the PI or designated sub-investigator trained by the PI. If an irritation score of 1 for any individual skin condition is observed, the subject will be excluded from the study.

Prior to the scheduled Treatment Day, subjects will undergo a minimum 14-day restriction. The subjects will be instructed to avoid contact with any topical or systemic antimicrobial products or any other product know to affect the normal microbial flora of the skin for the duration of their involvement in the study as written in the Subject Instructions for Main Study (Appendix 17.5.1).

If it becomes necessary to take systemic antibiotics or to apply topical medications to the test areas within this Washout period, the subject must contact the PI or designated sub-investigator whom will inform the PI as soon as reasonably possible so that another volunteer may be recruited.

Restrictions include, but are not limited to:

- Use of antimicrobial soaps, shampoos, lotions, perfumes, after shaves, colognes, antiperspirants, deodorants
- Contact with materials such as acids, bases, solvents
- Swimming in chemically treated pools and bathing in hot tubs, spas and/or whirlpools
- Use of tanning beds, hot waxes or depilatories (including shaving)

Subjects will be provided a kit with non-antimicrobial personal care products for exclusive use during the study.

If subjects require hair removal to facilitate sample collection, the subject will be asked to return to the test facility at approximately 48-96 hours prior to Treatment Day for clipping/re-clipping.

Prior to performing the clipping/re-clipping before the Treatment Day, a skin irritation assessment using the scale from Appendix 17.6 will be performed by the PI or designated sub-investigator trained by the PI. If an irritation score of 1 for any individual skin condition is observed, the subject will be excluded from the study.

Subjects will be required to refrain from bathing or showering 72 hours prior to Treatment Day.

5.1.2 Treatment Day

The PI or a designated sub-investigator will complete the Treatment Day Inclusion/Exclusion Criteria CRF. If these criteria are satisfied, a skin irritation assessment using the scale from Appendix 17.6 will be performed prior to performing the Treatment Day baseline sample collection, by the PI or designated sub-investigator trained by the PI. If an irritation score of 1 for any individual skin condition at the Treatment Day baseline is observed, the subject will be excluded from the study.

5.1.2.1 Preparation of Test Areas on Treatment Day

A Test Site Diagram for the groin test area is shown in Appendix 17.3.

5.1.2.1.1 Preparation of Groin Test Area

The test site within the groin region (groin test area) is defined as the inner aspect of the uppermost thigh, one inch parallel distance to the inguinal crease and where skin to skin contact is expected. Where subjects present with deep inguinal folds at the crease, the sampling distance from the crease may be increased to avoid skin folds in the sampling area. The corners of each groin test area will be marked directly on the skin using a non-toxic skin marker. Three sampling sites will be numbered within each groin test area, on each side of the groin region. The positioning and numbering of the groin sampling sites are standard for all subjects. Sampling sites on the contra-lateral side of the groin will be numbered in a mirror-image orientation. The three sampling sites within each test area represent one baseline (pre-prep) site and two post-prep sample sites (30 seconds and 10 minutes).

Test sites for the investigational product and active control applicator on the groin will be $1.5'' \times 5''$ (3.81 cm x 12.7 cm) in area, occur at the uppermost inner aspects of both thighs, and appear to be similar in condition.

After groin test areas are marked and sample sites numbered, baseline samples will be collected from the appropriate site per the randomization schedule in each test area using the scrub cup technique (section 5.2.1).

5.1.2.2 Study Products Application

The randomization schedule will designate the treatment to each side of the groin.

Following baseline sample collection, randomly assigned contra-lateral test areas will be treated with the applicable study products. The post-application sampling times will be randomized among the sampling sites within a test area.

The study products will be applied and the sampling configurations will be performed per the randomization scheme and the Treatment Application Instructions (Appendix 17.6). The duration of each application procedure will be recorded on the appropriate CRF. The study products, body area, application and dry times and treatment area are summarized in Table 2.

Products	Body Area	Application Time	Drying Time	Treatment Area
26 ml Project X (A)	Groin	120 seconds	min. 180 seconds	1.5" x 5.0" (3.81 cm x 12.7 cm)
10.5 ml Project X (B)	Groin	120 seconds	min. 180 seconds	1.5" x 5.0" (3.81 cm x 12.7 cm)
5.1 ml Project X (C)	Groin	120 seconds	min. 180 seconds	1.5" x 5.0" (3.81 cm x 12.7 cm)
Prevantics® Maxi Swabstick 5.1 ml (D)	Groin	120 seconds	90 seconds	1.5" x 5.0" (3.81 cm x 12.7 cm)

Table 2: Study products, body area, application and dry times and treatment area

5.1.2.3 Timing of Post Application Sample Collection

Microbial samples will be collected at 30 seconds (+5 seconds) and 10 minutes (± 30 seconds), post treatment application for both left side and right side. Post application timing begins upon completion of the study product application, including drying time. Microbial samples will be collected using the scrub cup technique (section 5.2.1).

A skin irritation assessment using the scale from Appendix 17.7 will be performed by the PI or designated sub-investigator trained by the PI prior to collection of each post treatment microbial sample

collection (30 seconds and 10 minutes) and a corresponding rating score for each individual skin condition will be recorded in the subject's CRF.

If an irritation score of 3 for any individual skin condition at any post treatment observation is assigned, the subject will be discontinued from the study and an adverse event will be recorded. See Section 8.3 (Adverse Events).

Following final sample collection, the remaining study material will be removed from the subjects' skin with water and soap as necessary and dried with paper towels.

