3.1 Overall Study Design and Plan

This study is designed to determine the antimicrobial effectiveness of three treatments (A, B and C), intended for use as Patient Preoperative Skin Preparation. The testing methods are based on the standardized test method ASTM E1173-15, Evaluation of Preoperative, Precatheterization, or Preinjection Skin Preparations, and using the requirements specified by in the 2017 FDA 21 CFR Part 310, Safety and Effectiveness of Health Care Antiseptics; Topical Antimicrobial Drug Products for Over-the-Counter Human Use, Final Rule (December 20, 2017). The immediate antimicrobial efficacy will be evaluated in this study.

At least 100 subjects will be treated bilaterally with two of the four test materials (A, B, C and Positive Control), one per each side of the groin test site. Subjects will undergo at least a 14-day washout period before Treatment Day. During Treatment Day subjects who meet the Inclusion Criteria will be treated with the study products and samples will be taken before and after treatment application. The cup scrub technique will be used for sampling baseline, 30-seconds and 10-minutes on the Treatment Day.

The immediate antimicrobial efficacy at 30 seconds and 10 minutes post-application will be demonstrated if the non-inferiority of the ATE of the investigational products (A, B and C) compared to Positive Control (D) is met (the upper two-sided 95% confidence bound of the post-application microbial counts corrected for Baseline of the investigational products A, B or C compared to the Positive Control should be less than 0.5 log₁₀).

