3.5 Study Products

The products identified in Table 1 will be used in the study. Specific product identification codes and lot numbers will be included with the clinical supplies when they are shipped to the Research facility.

Treatment Denomination Volume Description 26 ml Project X 26 ml 3.15 % w/v CHG / 70% v/v IPA В 10.5 ml Project X 10.5 ml 3.15 % w/v CHG / 70% v/v IPA С 5.1 ml Project X 5.1 ml 3.15 % w/v CHG / 70% v/v IPA 5.1 ml D Prevantics® Maxi Swabstick 3.15 % w/v CHG / 70% v/v IPA

Table 1: Study Products

PDI is responsible for analytically testing (content and purity) the study products to ensure they comply with their specifications and both released as per approved specifications of the marketed control product.

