3.6.2 Study Supplies Provided by Research facility

- Product kits (toiletry items to be used by subjects during study)
- Stripping Suspending Fluid with product neutralizers (SSF++) containing 1.01% Na₂HPO₄, 0.04% KH₂PO₄, 0.1% Triton X-100, 1.167% Lecithin, 10% Polysorbate 80, 0.5% Na₂S₂O₃ \bullet 5H₂O, and 1% TamolTM (pH 7.9 \pm 0.4)
- Butterfield's sterile phosphate-buffered water (PBW), 312 μ M KH₂PO₄ (pH 7.2 \pm 0.4)
- Trypticase soy agar containing 0.5% Polysorbate 80 and 0.07% lecithin (TSA+N)
- Disposable Pasteur Pipettes, sterile
- Tubes with sealable caps, polypropylene or glass, sterile
- Petri dishes, 90 mm, sterile
- Gloves, sterile
- Gauze, sterile
- Non-toxic marking pen: Chemo Skin Marker- Regular™
- Rubber policemen, sterile
- Scrub cups (2.20 cm I.D., 3.80 cm²), sterile
- Timers
- Pipette Aid or similar apparatus
- Vortex mixer
- Surgical Clipper & clipper blades: 3M Surgical Clipper
- Culture Media Preparator
- Peristaltic Pump
- Incubator (30 \pm 2°C)
- Disposable underwear for subjects
- urine pregnancy test (UPT)
- Biological safety cabinet

- Manual colony counter
- pH-meter

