5.2 Microbiological Methods

5.2.1 Microbial Sample Collection / Cup Scrub Technique

Quantitative cultures (treatment day baselines and post treatment samples) will be obtained by a modification of the cylinder sampling technique of Williamson-Kligman cup scrub technique following ASTM E1874-14 "Standard Test Method for Recovery of Microorganisms from Skin using the Cup Scrub Technique". To collect the samples, a sterile scrub cup (2.20 cm I.D.) will be placed on the site and held firmly to the skin. 3.0 ml of SSF++ will be pipetted into the cup and the skin will be scrubbed in a circular motion with moderate pressure for 1 minute using a sterile rubber policeman. Using a sterile transfer pipette, the SSF++ will be removed and placed in a sterile test tube. An additional 3.0 ml of fresh SSF++ will be pipetted into the cup and the scrub procedure will be repeated. This solution will be pooled with the first solution collected.

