9.3 Efficacy Analyses

An alpha level of 5% will be used for all analyses.

The following descriptive statistics for log_{10} CFU/cm² and for log_{10} CFU/cm² reductions from Baseline will be computed for each treatment, grouped by body area and each post application sampling time point (30 seconds, 10 minutes and/or Baseline, by case): mean, median, standard deviation, minimum, maximum, and count.

The statistician will be blinded to the treatment during the analysis phase.

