9.3.1 Efficacy Analysis

A linear regression model for each post treatment sampling time point of immediate efficacy (30 seconds and 10 minutes post-application) will be used. In the model, the dependent variable used will be the post treatment bacterial count (\log_{10} CFU/cm²) and predictors will be the treatment as a fixed effect and the Baseline as a covariate. The ATE corrected for Baseline will be estimated from the model and compared to non-inferiority criteria.

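### Does starting the sampling clock after each product's own drying period undermine the comparison with the active control?

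*Combined protocol and SAP*

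**What the plan says.** Section 5.1.2.3 defines time zero: "Post application timing begins upon completion of the study product application, including drying time". Samples are then due at 30 seconds (+5 s) and at 10 minutes (±30 s).

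Table 2 in section 5.1.2.2 gives 120 s of application for every product. Drying is at least 180 s for A, B and C and 90 s for D. The synopsis and section 17.5 give the same drying times and mark D's as approximate. The end state in section 17.5 is complete dryness for all four products.

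The claim is set in section 3.1: "The immediate antimicrobial efficacy at 30 seconds and 10 minutes post-application will be demonstrated if the non-inferiority of the ATE" of A, B and C to D is met, with a margin of 0.5 log10. Section 9.3.1 fits one regression per time point, in which "predictors will be the treatment as a fixed effect and the Baseline as a covariate". Section 9.3 adds descriptive statistics that "will be computed for each treatment, grouped by body area and each post application sampling time point".

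On recording, section 5.1.2.2 says: "The duration of each application procedure will be recorded on the appropriate CRF".

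**The concern.** All four products carry the same stated actives at the same strengths; the control is listed in section 3.5 as "Maxi Swabstick 3.15 % w/v CHG / 70% v/v IPA". The sampling fluid neutralizes the antiseptic (section 3.6.2: "Stripping Suspending Fluid with product neutralizers (SSF++) containing"), and section 5.2.1 has it enter at sampling: "3.0 ml of SSF++ will be pipetted into the cup". Exposure at a site therefore presumably ends when the cup is filled, and A-C have had longer exposure than D by then.

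If killing continues after the skin is dry, a pass on the non-inferiority test could owe something to later sampling and not only to the applicator and volume. The direction favours the investigational products. Two further points add to the unease. Section 3.1 does not repeat that the drying directions differ, and drying time and cup-placement time are not named separately as recorded items. At stake is what the result may be said to show: non-inferiority as directed, or non-inferiority at the same elapsed time.

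**Working it through.** **Inputs.** Application 120 s for all products; drying 180 s (a minimum) for A-C and 90 s (approximate) for D (Table 2, section 17.5). Sampling at 30 s (+5 s) and 600 s (±30 s) after drying (section 5.1.2.3). Margin 0.5 log10 (section 2.1). At least 50 evaluable sites per product (section 9.2).

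**The plan's own figures.** Section 17.5 reproduces Table 2. For A-C, two minutes of strokes is 120 s and three minutes of drying is 180 s. For D, 60 + 60 = 120 s of strokes, then about 90 s.

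**Elapsed time at sampling** (drying + sampling time; add 120 s to count from the start of application):

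| Sample | A-C from end | D from end | Ratio | A-C from start | D from start | Ratio |
|---|---|---|---|---|---|---|
| 30 seconds | 180 + 30 = 210 s | 90 + 30 = 120 s | 1.75 | 330 s | 240 s | 1.38 |
| 10 minutes | 180 + 600 = 780 s | 90 + 600 = 690 s | 1.13 | 900 s | 810 s | 1.11 |

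The gap is 90 s at both times. The skin is already wet with antiseptic during application, so the ratios from the start describe exposure better. With the sampling windows, the gap is 85 to 95 s at 30 seconds and 30 to 150 s at 10 minutes. Because 180 s is a minimum, 90 s is a floor if D dries for 90 s.

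**What 90 s could be worth.** The documents give no kill rate, so every fall below is an assumption. D's two samples are 690 − 120 = 570 s apart.

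- Linear fall F between them: shift = F × 90/570. F = 0, 0.3, 0.5 and 1.0 log10 give 0, 0.05, 0.08 and 0.16 log10.
- Fall of 1.0 log10 that levels off with half-life h: shift at 30 seconds = (1 − 2^(−90/h)) / (1 − 2^(−570/h)). For h = 60, 120, 300 and 600 s this gives 0.65, 0.42, 0.26 and 0.20 log10. At 10 minutes, multiply by 2^(−570/h): 0.00, 0.02, 0.07 and 0.11 log10.
- As a constant rate, 0.5 / 1.5 min = 0.33 log10 per minute would use the whole margin.

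**Error rate.** Assume a residual SD of 1.0, so that the standard error is √(2/50) = 0.2.

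- As-directed comparison, true difference at the margin: chance of passing = Φ(−1.96) = 2.5%, whatever the drying times.
- Pass misread as an equal-time claim, with a shift b favouring A-C: Φ(b/0.2 − 1.96). For b = 0.15 and 0.30 this is 11% and 32%.

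The second line concerns a claim that the plan does not make.

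**Could the analysis separate time from product?** At nominal drying the windows are 210-215 against 120-125 s, and 750-810 against 660-720 s. They do not overlap at either time. Elapsed time is almost fully confounded with product, so a time covariate in the section 9.3.1 model would not help.

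**The case for a change.** The strongest case for a change is that it would be cheap: one qualifying sentence in section 3.1, two time fields on the CRF, and perhaps an exploratory contrast of an investigational product's 30-second count with D's 10-minute count, to bound the equal-time difference. Staff who apply and sample are unblinded, A-C drying has no upper limit, and the end of drying starts the clock, so recorded times would let a reader verify the windows.

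The timing facts behind this stand. The additions gain little.

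- **The sentence.** Section 5.1.2.3 already defines post-application time as starting after drying, so the wording in section 3.1 carries that meaning. Nothing in the documents claims equal elapsed time.
- **The time fields.** Drying is a numbered step of the application instructions, and section 5.1.2.3 counts it within completion of application. The recorded duration can fairly be read to include it, although one total would not separate drying from strokes. Cup placement is held to stated windows. The CRF is not in the documents, so an item that is not named may still be recorded.
- **The contrast.** Section 9.3.1 fits each time point separately, so neither model yields a cross-time difference; a further model would have to be specified. The bound also needs mean counts to move in one direction between the two samples, which two time points cannot test. It has little power where the worry is real. In simulation with no true equal-time difference, SD 1.0 and 50 independent sites per product (all assumed), both bounds fell below 0.5 in about 24% of runs for a linear fall of 0.3 log10 and 6% for a fall of 0.5.
- **A request to justify the unequal drying times.** The synopsis, Table 2 and section 17.5 agree, apart from D's time being marked approximate in two of the three. There is no contradiction to reconcile.

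**Conclusion.** No change. The plan compares products as directed, with the clock starting at complete dryness in every arm. That is a legitimate design choice and is disclosed in three places. Followed as written, it gives a sound answer to the question it asks, and the 90 s gap leaves the 2.5% error rate of that comparison untouched.

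The gap itself is real: 210 against 120 s, and 780 against 690 s, after the end of application. It limits interpretation only. A pass does not show non-inferiority at equal elapsed time. How far the two readings could diverge depends on killing after drying, on which the documents are silent: nil if killing is complete by then, and larger at 30 seconds than at 10 minutes if it is continuing but slowing. The planned descriptive table will show how far D's counts move between its two samples, which tells the reader whether the distinction matters.

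A careful report author would state that the conclusion holds for each product under its own drying directions, and would tabulate whatever times the CRF holds. That is ordinary reporting practice and needs no amendment.
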